8.1. Study Drug Administration

Number of Sachets Dispensed and returned will be summarized overall and for each Period. In addition, the duration of treatment will be summarized overall and for each period.

8.1.1. Adverse Events

All adverse events will be coded using the Medical Dictionary for Regulatory Activities (MedDRA) Version 21.0 or greater. Treatment emergent adverse events (TEAEs) are defined as adverse events with onset dates on or after the first dose of study drug.

All AE summaries will include total number of TEAEs and total number of patients with AEs.

An overall summary of adverse events will include number (%) of patients reporting ≥ 1 TEAE (and number of TEAEs), TEAE by Severity (and number of TEAEs), treatment-related TEAEs (and number of TEAEs), SAEs (and number of TEAEs), TEAE by outcome (and number of TEAEs), TEAEs that resulted in treatment discontinuation (and number of TEAEs). In addition, the total number of TEAEs by subject will be summarized.

Additionally, summaries will be presented for all TEAEs by system organ class and preferred term (overall and by severity). TEAEs determined by the investigator to be treatment-related (overall and by severity). Serious AEs will also be summarized. Adverse events causing permanent discontinuation from treatment will be summarized, fatal adverse events will be summarized, and TEAEs by preferred term in descending order will be summarized.

The incidence of adverse events will be summarized using descriptive statistics by system organ class and preferred term. Patients are counted only once in each system organ class category, and only once in each preferred term category. Treatment-related adverse event summaries will include adverse events with missing relationship to study drug. For the summaries by severity, patients and TEAEs are counted at the greatest severity.

AEs will be summarized separately for each treatment Period (1, 2) and overall (the whole study).

Listings for fatal AEs, serious AEs, and AEs leading to discontinuation, will also be presented.

8.1.2. Vital Signs

Vitals signs at each visit and changes from baseline to each visit will be summarized using descriptive statistics.

8.1.3. Electrocardiogram

ECG parameters at each visit and changes from baseline to each visit will be summarized using descriptive statistics. In addition, shifts in ECG's (normal, abnormal not clinically significant, abnormal clinically significant) from baseline to each visit will be summarized descriptively.

8.1.4. Physical Examination

Shifts (normal, abnormal, NCS, and abnormal CS) from baseline to each visit will be summarized using patient counts for each category.

8.1.5. Neurological Examination/Targeted Neurological Examination

Shifts (normal, abnormal NCS, and abnormal, CS) from baseline to each visit collected will be summarized using patient counts for each category in the neurological examination.

8.1.6. Clinical Laboratory Tests

Clinical labs (Chemistry, Hematology, Urinalysis, and Testosterone) results at each visit and change from baseline to each visit will be summarized using descriptive statistics. In addition, clinically significant chemistry and hematology labs will be summarized. In addition, shift tables for chemistry and hematology will be prepared.

8.1.7. Concomitant Medications

All concomitant medications will be coded using WHO Drug. The incidence of concomitant medications will be summarized using descriptive statistics by therapeutic class and preferred term. Patients are counted only once in each therapeutic class category, and only once in each preferred term category. Concomitant medications will include all medications taken on or after Day 1.

Concomitant medications will be summarized separately for each treatment Period (1, 2) and overall (the whole study).

8.1.8. Patient Skin Irritation Score

The total number of patient skin irritation scores (0=No Skin redness to 4=Intense Redness with Blisters or Broken Skin) collected from the diary will be displayed within each treatment period overall and within 2-week intervals. The number of subjects with an assessment overall and within each 2-week period will be summarized. In addition, the total number of unique subjects for each category will be displayed.

8.1.9. Investigator Skin Irritation Score

The investigators skin irritation score (0=No Erythema to 4=Intense Erythema with Edema and Blistering/Erosion) for the left shoulder and upper arm and right shoulder and upper arm will be summarized using descriptive statistics.

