6. TRIAL OBJECTIVES AND PURPOSE

6.1. Primary Objective

Primary:

To evaluate the safety and tolerability of ZYN002 administered as a transdermal gel formulation, for up to 38weeks, in patients ages 4 to < 18 years, in the treatment of symptoms of 22q.11.2 Deletion Syndrome (22qDS).

Secondary:

- To evaluate the efficacy of ZYN002 in the treatment of symptoms of 22qDS.
- To evaluate CBD and THC plasma level exposure.

Exploratory:

The identification of plasma levels of CBD metabolite(s) may be conducted.

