- h. At Weeks 6, and 14 parents/caregivers will administer the dose in the clinic after they have their PK and valproic acid (for patients taking valproate/valproic acid) blood drawn. At Week 14 patients who require a tapering period will be provided a 1 or 2-week supply of study treatment.
- i. A skin assessment examination will be completed by the Investigator at Day 1 pre-dose. Shoulders and upper arms will be examined to determine there are no skin disease or condition, including eczema, psoriasis, melanoma, acne, contact dermatitis, scarring, imperfections, lesions, tattoos, or discoloration that may affect treatment application, application site assessments, or affect absorption of the study drug where study drug could be applied.
- j. Parents/caregivers will assess the application site daily and record all irritation scores in their daily skin irritation diary, starting with the PM dose on Day 1. When irritation exists, efforts will be made to apply the gel to a non-irritated area of the upper arms/shoulders and/or right and left upper thighs. Temporary application to the upper thighs can only be used after consultation with the investigator. If the skin irritation score is greater than "2", the patient will contact the Investigator to determine if an Unscheduled Visit is required.
- k. The investigator will perform a skin irritation examination pre-dose at study Visits 3, Visit 4/EOS/ET and Unscheduled Visits. The parent/caregiver will also be asked about the patients skin irritation at the Week 10 Telephone Follow-up call.
- l. A Telephone Follow-Up will occur for those patients whose dose was increased at Week 6.

Table 6: Period 2 Schedule of Assessments – 24-Week Extension Treatment

| Study Procedures | 24-Week Treatment Period 2 Visit Schedule | | | Taper Period, If Applicable | | Study Visit Week 40 or Week 41 for AED Patients Tapering Study Drug ^a | Un-scheduled Visit(s) |
|---|--|--------------------------------------|---|--|---------------------------|---|--------------------------|
| | Visit 5 Week 22 (± 3 days) | Visit 6 Week 30 (± 3 days) | Visit 7 Week 38 EOS/ET ^a (± 3 days) | Week 39 (± 3 days) | Week 40 (± 3 days) | | |
| | Study Drug Dosing | | | Tapered 50% each week. No Study Visit | | | |
| Concomitant Medications | X | X | X | | | X | X |
| Physical/Neurological Exam ^b | | | X | | | X | |
| Vital Signs ^c | X | X | X | | | X | X |
| 12-lead ECG | | | X | | | | |
| Laboratory Tests and Urinalysis | | | X | | | | |

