7.6.13. Investigator Skin Irritation Examination

The investigator will conduct a skin irritation examination pre-dose of the application site(s) at Week 6, Week 14, and Week 38 EOS/ET, and Unscheduled Visits. In addition, parents/caregivers will be asked about skin irritation at the Week 10 Telephone Follow-up call. When excessive skin redness is noted, efforts will be made to temporarily apply the gel to a non-red area of the upper arms/shoulders and/or right/left thighs at the approval of the investigator. The investigator will use discretion in suspending dosing for patients with a skin redness score of '4' (intense erythema) but will in all score of '4' cases immediately (within 24 hours) complete an adverse event report and contact their study CRA and the Sponsor Medical Monitor.

Application of ZYN002 to the right or left thigh should be viewed as a temporary alternate application site only until the redness on the upper arms/shoulders is reduced.

Patients having a skin irritation score > '0' at Week 38 will continue to be followed through Unscheduled Visits until the skin irritation score is recorded as '0' (no erythema). At this time, the patient will be discharged from the study.

Refer to [Table 7](#) for the Skin Irritation Scale to be used for skin redness examinations.

Table 7: Skin Irritation Scale

| Score | Definition |
|-------|--|
| 0 | No erythema |
| 1 | Minimal erythema |
| 2 | Moderate erythema with sharply defined borders |
| 3 | Intense erythema with or without edema |
| 4 | Intense erythema with edema and blistering/erosion |

A de-identified picture of an application site may be taken at the discretion of the Principal Investigator.

Should the patient experience dry skin at the application sites, moisturizing lotion (Cetaphil) which will be supplied by the Sponsor, may be applied two hours post gel application.

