11.2.1. Definition of Adverse Events

11.2.1.1. Adverse Event

An AE is an undesirable medical occurrence (sign, symptom, or diagnosis) or worsening of a pre-existing medical condition (e.g., diabetes, congestive heart failure, rheumatoid arthritis, psoriasis) that occurs at any time after signing of the ICF whether or not it is considered to be related to treatment. Worsening of an existing medical condition is when a condition present at the time of signing of the ICF (e.g., cancer, diabetes, gout) becomes more severe, more frequent, or increased in duration during the study. Hospitalizations for pretreatment conditions (e.g., elective cosmetic procedures) or surgeries that were planned before entry into the study are not considered AEs.

The Investigator is responsible for reviewing laboratory test results and determining whether an abnormal value represents for the patient a change from the time of signing of the ICF. In general, abnormal laboratory findings without clinical significance (based on the Investigator's judgment) should not be recorded as AEs. Clinically significant changes occurring after the signing of the ICF are considered AEs; however, the reported adverse event should include the underlying diagnosis or resulting clinical sequelae. Patients having clinically significant AEs will be followed until they return to normal or become stabilized.

Throughout the study, the Investigator will monitor each patient for evidence of drug intolerance and for the development of clinical and/or laboratory evidence of an adverse event. An AE assessment will be made by the Investigator on a routine basis throughout the study. All AEs which occur during the course of the study must be reported in detail on the appropriate CRF

page and on any other report form required by national law. All TEAEs must be followed to a satisfactory resolution.

All AEs will be collected from study Screening until the patient is discharged from the study.

Application site irritation scores of 1, 2, or 3 should not be recorded as AEs but will be assessed and recorded as part of the skin irritation score examinations. Skin irritation recorded with a score of '4' (as assessed by the Investigator) will be recorded as part of the skin irritation examination, and will also be recorded by the Investigator as an AE. The Investigator should report as an expedited AE (within 24 hours of assessment) to the Sponsor.

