If a patient reports a worsening of skin irritation after a period of improvement, the Investigator should assess whether the event is indicative of a delayed hypersensitivity reaction. If in the opinion of the Investigator the event is a delayed hypersensitivity reaction, this will be recorded as an AE.

All study drug application site signs/symptoms will be recorded as AEs. The event term should specify "application site disorder - [specify sign or symptom]".

If a patient becomes pregnant during or after exposure to a study drug received in this study, the investigator will immediately discontinue the patient from the study and contact the Sponsor or designee. The investigator will complete the Sponsor's (or designee's) Clinical Pregnancy Notification Form and email it to the Sponsor within two days of learning of the pregnancy. Diligent efforts will be made to determine the outcome for all pregnancy exposures in the clinical study. Information on the status of the mother and the child will be forwarded to the Sponsor.

Generally, follow-up will occur within 6 to 8 weeks following the estimated delivery date. Any premature termination of the pregnancy will be reported. Both maternal and paternal exposure will be collected. For exposure involving the female partner of a male participant, the necessary information must be collected from the participant, while respecting the confidentiality of the partner.

Although pregnancy occurring in a clinical study is not considered to be an AE or SAE, any pregnancy complication or elective termination of a pregnancy for medical reasons will be recorded as an AE or SAE and will be followed as such. All reports of congenital abnormalities/birth defects are SAEs. Spontaneous miscarriages should also be reported and handled as SAEs. Elective abortions without complications should not be handled as AEs.

The date of onset and resolution of the adverse event will be collected.

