13.5. Statistical Methods

Descriptive statistics (mean, median, standard deviation, minimum, and maximum) for continuous data and number (n) and percentage (%) for categorical data will be presented for all efficacy and safety parameters.

All efficacy assessments will be summarized at Weeks 6, 14, 22, 30, and 38.

Vital sign assessments (actual and change from screening) taken at study Day 1, Weeks 6, 14, 22, 30, and 38 will be summarized using descriptive statistics and presented by maintenance dose.

ECGs (actual and change from Screening) will be summarized by actual treatment group. ECG results including any clinically significant findings will be summarized at each study visit.

Safety laboratory and urinalysis assessments taken at Week 6, 14, and Week 38 (actual and change from screening) will be summarized by treatment at the time of the assessment.

Application site irritation will be summarized using counts and percentages for each respective site irritation score (0, 1, 2, 3, or 4) by dose at the time of assessment.

AEs will be tabulated by the actual treatment dose of study drug received at the time of initiation of the adverse event and classified by system organ class and preferred term using the Medical Dictionary for Regulatory Activities (MedDRA). Additionally, AEs will be tabulated overall (total number of AEs and total number of patients with AEs).

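### The SAP's investigator skin-irritation summary leaves out the thighs, and two protocol sentences disagree on whether scored irritation is an adverse event

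*SAP*

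**What the plan says.** **Objective.** Protocol 6.1: "To evaluate the safety and tolerability of ZYN002 administered as a transdermal gel formulation".

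**Where the investigator looks.** Protocol 7.6.13: "The investigator will conduct a skin irritation examination pre-dose of the application site(s) at Week 6, Week 14, and Week 38 EOS/ET". The same section says that when redness is excessive, "efforts will be made to temporarily apply the gel to a non-red area of the upper arms/shoulders and/or right/left thighs". Footnote j to protocol Table 5 adds a condition: "Temporary application to the upper thighs can only be used after consultation with the investigator".

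**How scores are to be summarised.** Protocol 13.5: "Application site irritation will be summarized using counts and percentages for each respective site irritation score", that is 0 to 4, by dose at the time of assessment. No body site is named. SAP 8.1.9 says the investigator's score "for the left shoulder and upper arm and right shoulder and upper arm will be summarized using descriptive statistics". SAP section 10 identifies no changes from the protocol.

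**What counts as an AE.** Protocol 11.2.1.1: "Application site irritation scores of 1, 2, or 3 should not be recorded as AEs". A score of 4 is recorded as an AE and reported on an expedited basis. A little further on, the same section says: "All study drug application site signs/symptoms will be recorded as AEs". It states no exception for irritation that is already scored.

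**Interim.** SAP 5.1 produces the displays marked X in section 11. Tables 14.3.8.1 (diary scores) and 14.3.8.2 (investigator scores) have no X, and skin scores are not in the list of interim data. SAP 5.1 does allow ad hoc tables.

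**The concern.** There are two separate gaps in how application-site tolerability is measured.

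The first is in the SAP. Gel moves to the thighs because the arms are irritated, so the patients whose treated skin drops out of SAP 8.1.9 are selected for having had irritation. Their arms stay in the table, while the skin receiving gel does not. In this table the error can only run one way: leaving out a site can lower a patient's worst score or leave it unchanged, never raise it.

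The second is in the protocol. Erythema is an application-site sign. One sentence keeps scores 1 to 3 out of the AE record, and another puts every application-site sign into it. Score 3 on the protocol's scale is intense erythema, with or without edema, so the conflict is not confined to trivial findings. Two study sites can see the same skin and record it differently, and both can cite the protocol.

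The gaps compound. If a study site follows the sentence excluding scores 1 to 3, a thigh score in that range appears in neither the AE tables nor the investigator summary.

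**Working it through.** The documents give no expected irritation rate and no sample size calculation, so there is no planned figure to reproduce. The check is a comparison of text, followed by a rough sizing.

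**Step 1: site coverage, output by output.**

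| Output | Body sites | Form |
|---|---|---|
| Protocol 13.5 plan | not restricted | counts and percentages, 0 to 4 |
| SAP 8.1.9 | shoulders and upper arms, left and right | descriptive statistics |
| SAP 8.1.8 (caregiver diary) | not restricted | score counts and unique subjects per score, by period and 2-week interval |
| Listing 16.12.2 | not restricted | patient-level listing |

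SAP 8.1.9 is narrower than the protocol, and the narrowing is not declared.

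**Step 2: AE status by score.** Call the sentence excluding scores 1 to 3 rule A, and the sentence covering all signs and symptoms rule B.

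| Finding | Rule A | Rule B |
|---|---|---|
| Score 1, 2 or 3 | not an AE | AE |
| Score 4 | AE, expedited | AE, expedited |
| Dryness, itch, pain | not addressed | AE |

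The conflict is confined to scores 1 to 3. Compared with uniform recording under A, mixed practice raises the AE count. Compared with uniform recording under B, it lowers the count.

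**Step 3: how often the thighs would be in use at a visit.** The only switch that the documents describe is in protocol 5.3.2: one patient in a 20-patient paediatric study (ZYN2-CL-009, 12-week period, 84 days) used the thighs for 6 days. Three assumptions are needed: this study resembles that one, there were no unreported switches, and timing is unrelated to visits.

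- Share ever switched: 1/20 = 5%, exact (Clopper-Pearson) 95% interval 0.1% to 24.9%.
- Share of days on the thighs for a switched patient: 6/84 = 0.071.
- Expected number on the thighs at one visit: 20 × 0.05 × 0.071 = 0.07 (range 0.002 to 0.36).
- Expected patient-visits over Weeks 6, 14 and 38 if all 20 attend all three: 3 × 0.07 = about 0.2 (range 0.005 to 1.1). This is generous, because Period 2 takes only patients with at least 35% improvement in irritability.
- Chance that at least one of 20 ever switches at a 5% rate: 1 − 0.95^20 = 64%.

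**Step 4: effect of one affected patient.** 1/20 = 5 percentage points. For illustration, if 6 of 20 patients had irritation at a visit and one had it only on the thighs, the table would show 5/20 = 25% instead of 6/20 = 30%. The full 5 points require that patient's arms to score 0.

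**The case against.** The strongest reply is that the SAP has a second, wider summary. The diary is scored every evening, and SAP 8.1.8 counts unique subjects at each score by period and 2-week interval, with no body-site limit. Peaks between clinic visits and thigh irritation can both show up there. A score above 2 prompts contact with the study site about an unscheduled visit, and a score of 4 is always an AE. Most of this stands and is why the effect is rated small. It does not remove the gap: the diary is rated by caregivers, and a listing gives no rate.

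Four stronger readings are tempting, but the documents do not support them.

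- **That irritation is undercounted.** The text shows only that it can be. Thigh use is optional, temporary and needs investigator consultation, and moving to a non-red part of the arms or shoulders is the alternative.
- **That the worst patients will look improved.** Thigh use lasts only until arm redness is reduced. A patient on the thighs at a visit may well still have red arms, and that score is summarised.
- **That means of a 0 to 4 scale will hide peaks.** SAP 8.1.9 does not mention means. SAP section 6 defines descriptive statistics for categorical variables as counts and percentages.
- **That the AE conflict shows undercounting, or swings the rate from 0% to 100%.** It can move counts either way, and such extremes are hypothetical. Rule B may have been meant for dryness, itch and pain, which earlier ZYN002 studies reported as TEAEs, but the sentence does not say so.

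**Conclusion.** The point holds as two limited gaps. The SAP's investigator summary omits a body site that the protocol allows for irritated patients, without declaring the change. It can therefore understate irritation at treated skin, by at most 5 percentage points per affected patient at N=20. Sizing from the single documented switch puts well under one patient on the thighs at any one visit, so the likely effect is small. That sizing rests on one patient in another study.

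The AE recording conflict is certain as worded. Its size is unknown and its direction open, because it depends on what each study site did. It matters most at the interim. Unless an ad hoc table is requested, application-site tolerability there rests on the AE tables alone, which are the outputs affected by the conflict.

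The study is exploratory and no formal test depends on these tables. The case for acting is that tolerability is part of the primary objective and the correction is cheap. The CRF and the diary form are not in the documents, so whether a thigh score or the site scored was captured cannot be checked.

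**What to change.** 1. **SAP 8.1.9 and Table 14.3.8.2.** Give counts and percentages for scores 0 to 4, using each patient's worst score over all application sites in use at the visit, with the thighs included where recorded. Report the number of patients ever switched to the thighs.
2. **SAP section 11.** Mark Tables 14.3.8.1 and 14.3.8.2 for the Period 1 display.
3. **Protocol 11.2.1.1.** Reconcile the two sentences into one recording rule. This review does not say which should prevail. The Note to File at the front of the SAP, effective 16 February 2026, speaks of how data were collected. If collection is over, the report should state which rule each study site followed.
4. **One added table.** Show patients with an application-site AE or an irritation score of 3 or higher. The part of the rate at score 3 or higher then no longer depends on which sentence a study site followed. Scores 1 and 2 remain affected by the recording rule, but are visible in the score tables.

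The cost is SAP wording, one extra table, some minor programming and one clarification to study sites. Thigh scores can be included only if the CRF captured them; if it did not, the report should say so.
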